11.5 Study Monitoring Requirements

It is the responsibility of the Investigator to ensure that the study is conducted in accordance with the protocol, ICH GCP, Directive 2001/20/EC, applicable regulatory requirements, and the Declaration of Helsinki (Seoul 2008) and that valid data are entered into the eCRFs.

The role of the study monitor is to verify the rights and well-being of the subjects are protected, the data is accurate, complete, and verifiable from source documents, and the conduct of the study is in compliance with the protocol, Declaration of Helsinki, ICH GCP, and applicable regulatory requirements.

To achieve this objective, the monitor's duties are to aid the Investigator and, at the same time, the Sponsor in the maintenance of complete, legible, well organized and easily retrievable data. Before the enrollment of any subject in this study, the Sponsor or their designee will review with the Investigator and site personnel the following documents: protocol, Investigator's Brochure, eCRFs and procedures for their completion, informed consent process, management of investigational product, and the procedure for reporting adverse events such as SAEs.

The Investigator will permit the Sponsor or their designee to monitor the study as frequently as deemed necessary to determine that data recording and protocol adherence are satisfactory. During the monitoring visits, information recorded on the eCRFs will be verified against source documents and requests for clarification or correction may be made. After the eCRF data is entered by the site, the CRA will review the data for safety information, completeness, accuracy, and logical consistency. Computer programs that identify data inconsistencies may be used to help monitor the clinical study. If necessary, requests for clarification or correction will be sent to investigators. The Investigator and his/her staff will be expected to cooperate with the monitor and provide any missing information, whenever possible.

All monitoring activities will be reported and archived. In addition, monitoring visits will be documented at the investigational site by signature and date on the study-specific monitoring log and findings documented in a follow-up letter.

11.6 Disclosure of Data

Data generated by this study must be available for inspection by the FDA, the Sponsor or their designee, applicable foreign health authorities, and the IRB/EC as appropriate. Subjects or their legal representatives may request their medical information be given to their personal physician or other appropriate medical personnel responsible for their welfare.

Subject medical information obtained during the study is confidential and disclosure to third parties other than those noted above is prohibited.

11.7 Retention of Records

To enable evaluations and/or audits from regulatory authorities or the Sponsor, the Investigator will keep records, including the identity of all participating subjects (sufficient information to link records, e.g., eCRFs and hospital records), all original signed ICFs, copies of all eCRFs, SAE forms, source documents, and detailed records of treatment disposition. The records should be retained by the Investigator according to specifications in the ICH guidelines, local regulations, or as specified in the Clinical Study Agreement, whichever is longer. **The**

Investigator must obtain written permission from Gemphire before disposing of any records, even if retention requirements have been met.

If the Investigator relocates, retires, or for any reason withdraws from the study, the Sponsor should be prospectively notified. The study records must be transferred to an acceptable designee, such as another Investigator, another institution, or to the Sponsor.

11.8 Publication Policy

Following completion of the study, the data may be considered for publication in a scientific journal or for reporting at a scientific meeting. Each Investigator is obligated to keep data pertaining to the study confidential. The Investigator must consult with the Sponsor before any study data are submitted for publication. The Sponsor reserves the right to deny publication rights until mutual agreement on the content, format, interpretation of data in the manuscript, and journal selected for publication are achieved.

11.9 Financial Disclosure

Clinical Investigators are required to provide financial disclosure information to the Sponsor to permit the Sponsor to fulfill its obligations under 21 CFR §54. In addition, investigators must commit to promptly updating this information if any relevant changes occur during the study and for a period of 1 year after the completion of the study.

11.10 Insurance and Indemnity

In accordance with the relevant national regulations, the Sponsor has taken out clinical trial insurance. This insurance provides coverage to the Sponsor in the event of physical injury or death related to the study drug or any procedure related to the protocol.

11.11 Legal Aspects

The clinical study is submitted to the relevant national competent authorities in all participating countries to achieve a clinical trial authorization (CTA).

The study will commence (i.e., initiation of study centers) when the CTA and favorable Ethics opinion have been received.

11.12 Definition of End of Study

The End of Study is defined as the completion of the Follow-up Visit or the ET Visit, if applicable.

11.13 Sponsor Discontinuation Criteria

Premature termination of this study may occur because of a regulatory authority decision, change in opinion of the IRB/EC, drug safety problems, or at the discretion of Gemphire. In addition, Gemphire retains the right to discontinue development of gemcabene at any time.

If a study is prematurely terminated or discontinued, Gemphire will promptly notify the Investigator. After notification, the Investigator must contact all participating subjects within 2 weeks. As directed by Gemphire, all study materials must be collected and all eCRFs completed to the greatest extent possible.

12 STUDY ADMINISTRATIVE INFORMATION

12.1 Protocol Amendments

Any amendments to the study protocol will be communicated to the investigators by PI [REDACTED] or the Sponsor. All protocol amendments will undergo the same review and approval process as the original protocol. A protocol amendment may be implemented only after it has been approved by the IRB, unless immediate implementation of the change is necessary for subject safety. In this case, the situation must be documented and reported to the IRB within 5 working days.

APPENDIX A: SCHEDULE OF PROCEDURES

	Pre-Screening ^a	Screening ^b	Treatment Period ^c					Follow-up ^d	ET
		up to Day -14	Day 1 ^e	Week 2 (Day 15± 3 days)	Week 4 (Day 29± 3 days)	Week 8 (Day 57± 3 days)	Week 12 (Day 85, or up to 3 days earlier)	Day 113 ± 3 days	
		Visit S1	Visit T1	Visit T2	Visit T3	Visit T4	Visit T5		
Informed consent	X	X ^f							
Inclusion/exclusion criteria	X	X							
Medical/surgical history and demographics	X	X ^f							
Full physical examination ^g	X	X ^f					X		X
Symptom-directed physical examination		X ^h	X	X	X	X		X ⁱ	
Vital signs ^j , height ^k , and weight	X	X	X	X	X	X	X		X
Body Mass Index (BMI)	X	X							
Urinalysis ^l	X	X	X		X	X	X	X ⁱ	X
Serum/urine pregnancy test ^m	X	X	X	X	X	X	X		X
Safety chemistry panel, coagulation, and hematology ⁿ	X	X	X	X	X	X	X	X ⁱ	X
TSH, HbA1c, and serology ^o	X	X ^f					X		X
Fasting lipid panel ^p ; LDL-C ultracentrifugation when necessary	X ^q	X	X	X	X	X	X		X
Fasting apolipoproteins ^r			X		X	X	X		X
CI			X				X		X
hsCRP, SAA, fibrinogen, and adiponectin			X				X		X
Fasting plasma glucose, insulin			X				X		X
Randomization			X						
Study drug administration ^s			X	X	X	X	X		
Dispense study drug and instructions			X	X	X	X			
Compliance check				X	X	X	X		X
Dietary instructions ^t	X	X	X	X	X	X			
12-lead ECG ^u		X	X	X	X	X	X		X
Initiate wash-out	X								
Adverse events	X ^v	X ^v	X	X	X	X	X	X	X

Concomitant medications	X	X ^f	X	X	X	X	X	X	X
Reserve samples			X	X	X	X	X		X

Footnotes appear on the following page

- a. Only subjects requiring a wash-out period will participate in the Pre-Screening Visit. Specifically, PCSK9 inhibitors will require an 8-week wash-out period, fibrates will require a 6-week wash-out period, and niacins or other lipid-regulating therapies such as bile acid sequestrants will require a 4-week wash-out period, prior to the Screening Visit.
- b. All eligible subjects will participate in the Screening Visit up to 14 days prior to Day 1. For subjects taking the required stable statin therapy for >4 weeks at the Screening Visit and do not require a wash-out period, the Screening Visit will be their first study visit.
- c. Study assessments will be completed ± 3 days of given time point for all study visits from Day 1 through Week 8. Week 12 assessments can be performed up to 3 days prior to Week 12, but not after Week 12.
- d. The Follow-up Visit will be conducted as a telephone call 4 weeks (± 3 days) after the last dose of study drug, unless the subject requires a site visit due to an abnormal result at Week 12 (or the ET Visit, if applicable) or an ongoing treatment-related adverse event.
- e. Procedures will be performed pre-dose. The Investigator will inquire with the subject at Day 1 to determine if there have been any changes in the subject's health affecting eligibility or requiring an update to their medical and surgical history.
- f. For subjects who required a wash-out period and completed the Pre-Screening Visit, the following Screening Visit procedures will not be repeated: informed consent, full physical examination, height, TSH, HbA1c, and serology (HBV, HCV, and HIV) screening. Updates, as needed, will be made to medical/surgical history, demographics, and concomitant medications.
- g. A full physical examination includes genitourinary examination per the Investigator's discretion and does not include a rectal examination.
- h. Only for subjects who required a wash-out period and completed the full physical examination at the Pre-Screening Visit.
- i. Only for subjects who had an abnormal result at Week 12 (or the ET Visit, if applicable) or an ongoing treatment-related adverse event.
- j. Vital signs include pulse rate, blood pressure, respiration rate, and temperature. Blood pressure should be obtained in the seated position, after the subject has rested comfortably for at least 5 minutes. Blood pressure at the Screening Visit should be obtained in both arms and the arm with the highest value should be used for ongoing monitoring throughout the rest of the study. If an automated assessment is performed, the same machine should be used for the subject throughout the study when possible. Care should be taken to ensure an appropriate cuff size is utilized.
- k. Height will be measured only at the subject's first study visit, either at the Pre-Screening Visit or the Screening Visit.
- l. A urine microscopic examination will be performed when the dipstick result is abnormal (positive for blood, leukocyte esterase, or nitrites). Urine protein:creatinine ratio (albumin:creatinine) will be performed at the Screening Visit, Day 1, Week 4, Week 12, the Follow-up Visit (only for subjects who had an abnormal result at Week 12 [or the ET Visit, if applicable] or an ongoing treatment-related adverse event), and the ET Visit, if applicable. Urinary NGAL will be measured at Day 1, Week 4, Week 12, the Follow-up Visit (only for subjects who had an abnormal result at Week 12 [or the ET Visit, if applicable] or an ongoing treatment-related adverse event), and the ET Visit, if applicable.
- m. For women of child-bearing potential only, a serum pregnancy test will be conducted at the Screening Visit, Week 12, and the ET Visit, if applicable. A urine pregnancy test will be conducted at the Pre-Screening Visit, Day 1, Week 2, Week 4, and Week 8.
- n. Clinically significant abnormal creatinine results at Week 12 (or the ET Visit, if applicable) will also be followed-up 2 weeks (± 3 days) after the last dose of study drug in addition to the Week 4 (± 3 days) Follow-up Visit. See [Appendix B](#) for a list of analytes and description of when repeat or reflexive testing will be required.
- o. Thyroid-stimulating hormone, HbA1c, and serology (HBV, HCV, and HIV) will be measured at the subject's first study visit, either at the Pre-Screening Visit, if applicable, or the Screening Visit. Only HbA1c will be measured at Week 12, and the ET Visit, if applicable.
- p. Includes LDL-C, non-HDL-C, TC, TG, HDL-C, and VLDL-C. Fasting will be defined as no food or caloric beverage for at least 10 hours prior to sample collection. Subjects will be permitted to have water.
- q. Includes LDL-C and TG only. Fasting will be defined as no food or caloric beverage for at least 10 hours prior to sample collection. Subjects will be permitted to have water.
- r. Includes ApoB, ApoA-I, ApoA-II, ApoA-V, ApoC-II, ApoC-III, ApoE, and Lp(a). Fasting will be defined as no food or caloric beverage for at least 10 hours prior to sample collection. Subjects will be permitted to have water.
- s. Study drug will be administered at the site on Day 1. Subjects will self-dose at all other times during the Treatment Period.
- t. Subjects will be counseled on a low-fat, low-cholesterol diet (NCEP ATP-III guidelines or equivalent).
- u. Subjects should be lying quietly in a fully supine position for at least 10 minutes prior to each 12-lead ECG.

- v. Serious adverse events that occur prior to the first dose of study drug (Day 1) should be reported as an update to medical history as well as be reported on the appropriate adverse event eCRF.

Apo = apolipoprotein; ECG = electrocardiogram; eCRF = electronic case report form; ET = Early Termination; HBV = hepatitis B virus; HbA1c = hemoglobin A1c; HCV = hepatitis C virus; HDL-C = high-density lipoprotein cholesterol; HIV = human immunodeficiency virus; HoFH = homozygous familial hypercholesterolemia; hsCRP = high-sensitivity C-reactive protein; LDL-C = low-density lipoprotein cholesterol; Lp(a) = lipoprotein(a); NCEP ATP-III = National Cholesterol Education Program Adult Treatment Panel III; NGAL = neutrophil gelatinase-associated lipocalin; non-HDL-C = non-high-density lipoprotein cholesterol; [REDACTED] [REDACTED] TC = total cholesterol; TG = triglyceride; TSH = thyroid-stimulating hormone; VLDL-C = very low-density lipoprotein cholesterol.

APPENDIX B: CLINICAL LABORATORY ANALYTES

Standard Safety Chemistry Panel

Alanine aminotransferase	Albumin
Alkaline phosphatase	Aspartate aminotransferase
Bicarbonate	Blood urea nitrogen
Calcium	Chloride
Creatine kinase	Creatinine [1]
Gamma-glutamyl transferase	Glucose
Lactate dehydrogenase	Phosphorus
Potassium	Sodium
Total bilirubin [2]	Total protein
Estimated glomerular filtration rate (GFR) [3]	

1. For a creatinine increase of >0.3 mg/dL (27 μ mol/L) from baseline during the study, repeat chemistry will be performed.
2. If total bilirubin is elevated, reflexive direct bilirubin testing will be performed.
3. For an estimated GFR decrease of >15 mL/min from baseline during the study, repeat chemistry will be performed.

Additional Chemistry Parameter

Glycosylated hemoglobin (HbA1c)
Fasting plasma glucose
Fasting insulin

Endocrinology

Thyroid-stimulating hormone

Hematology

Hematocrit	Hemoglobin [1]
Platelet count	Red blood cell count
Mean corpuscular hemoglobin concentration	Mean corpuscular hemoglobin
White blood cell count and differential (basophils, eosinophils, lymphocytes, monocytes, and neutrophils) [2]	Mean corpuscular volume

1. For a hemoglobin decrease of >1.5 g/dL from baseline during the study, repeat hematology studies and reflexive evaluation of reticulocyte count will be performed.
2. Manual microscopic review is performed only if white blood cell count and/or differential values are out of reference range.

Urinalysis [1]

pH
Ketones
Leukocyte esterase
Glucose
Nitrite
Albumin

Proteinuria [2]
Blood
Specific Gravity
Bilirubin
Neutrophil gelatinase-associated lipocalin (NGAL) [3]

1. A urine microscopic examination will be performed when dipstick results are abnormal (positive for blood, leukocyte esterase, or nitrites).
2. Urine protein:creatinine ratio (and albumin:creatinine ratio) will be performed at the Screening Visit, Day 1, Week 4, Week 12, the Follow-up Visit (only for subjects who had an abnormal result at Week 12 [or the ET Visit, if applicable] or an ongoing treatment-related adverse event), and the ET Visit, if applicable.
3. Urinary NGAL will be measured at Day 1, Week 4, Week 12, the Follow-up Visit (only for subjects who had an abnormal result at Week 12 [or the ET Visit, if applicable] or an ongoing treatment-related adverse event), and the ET Visit, if applicable.

Pregnancy Test

Serum and urine pregnancy tests will be administered to all female subjects of child-bearing potential.

Serology

Hepatitis B
Human Immunodeficiency Virus

Hepatitis C

Coagulation

Prothrombin time
International normalized ratio

Activated partial thromboplastin time

Efficacy Parameters

The following efficacy parameters will be assessed in this study:

Apolipoprotein (Apo) A-I
ApoB
ApoC-III
ApoC-II
High-density lipoprotein cholesterol
Non-high-density lipoprotein cholesterol
Triglycerides
High-sensitivity C-reactive protein
CCI
Adiponectin

ApoA-II
ApoA-V
ApoE
Lipoprotein (a)
Low-density lipoprotein cholesterol
Very low-density lipoprotein cholesterol
Total cholesterol
Serum amyloid A
Fibrinogen

APPENDIX C: NEW YORK HEART ASSOCIATION CONGESTIVE HEART FAILURE CLASSIFICATION

- Class I: subjects with cardiac disease but without resulting limitation of physical activity. Ordinary physical activity does not cause undue fatigue, palpitation, dyspnea, or anginal pain.
- Class II: subjects with cardiac disease resulting in slight limitation of physical activity. They are comfortable at rest. Ordinary physical activity results in fatigue, palpitation, dyspnea, or anginal pain.
- Class III: subjects with cardiac disease resulting in marked limitation of physical activity. They are comfortable at rest. Less than ordinary activity causes fatigue, palpitation, dyspnea, or anginal pain.
- Class IV: subjects with cardiac disease resulting in inability to carry on any physical activity without discomfort. Symptoms of heart failure or the anginal syndrome may be present even at rest. If any physical activity is undertaken, discomfort is increased.

Source: The Criteria of the New York Heart Association. Nomenclature and Criteria for Diagnosis of the Heart and Great Vessels. 9th ed. Boston, Mass: Little, Brown & Co; 1994:253-256.

**APPENDIX D: CYTOCHROME P450 3A4 INHIBITORS:
EXCLUSIONARY MEDICATIONS**

Amiodarone
Atazanavir
Clarithromycin
Darunavir
Diltiazem
Fluconazole
Fosamprenavir
Imatinib
Itraconazole
Lopinavir
Mibefradil
Nelfinavir
Ritonavir
Telithromycin
Troleandomycin
Voriconazole

Amprenavir
Cimetidine
Conivaptan
Delavirdine
Erythromycin
Fluvoxamine
Grapefruit juice
Indinavir
Ketoconazole
Miconazole
Nefazodone
Posaconazole
Saquinavir
Tipranavir
Verapamil

APPENDIX E: MUSCLE INJURY AND HEPATIC MONITORING

Muscle Injury

Muscle injury will be assessed using a combination of clinical signs and symptoms and laboratory data (creatinine kinase [CK], hepatic, and renal function).

All subjects with suspected or confirmed muscle injury should be managed according to the standard of care at the discretion of the Investigator.

- Subjects with new or unexplained muscle symptoms should have an unscheduled visit scheduled within 7 days of site notification. At this visit, samples should be sent for a full chemistry panel, including CK, liver, and renal function.
- Subjects with CK elevations of $>3 \times$ upper limit of normal (ULN) who are asymptomatic should be considered for an unscheduled visit (+ isozymes), based upon medical judgment.
- All subjects with CK elevations $>10 \times$ ULN should have an unscheduled visit (+ isozymes). Study drug should be temporarily discontinued, pending the results of an investigation into the cause of muscle injury and/or CK elevation is complete.

It is important that subjects are instructed to not undertake any form of strenuous physical activity for at least 24 hours prior to repeat blood testing.

Hepatic Monitoring

Subjects with hepatic enzyme elevations should be managed according to the standard of care, at the discretion of the Investigator. For subjects with signs or symptoms suggestive of hepatitis, an unscheduled visit and a chemistry panel should be performed. Subjects with an alanine aminotransferase (ALT) $>2 \times$ ULN with symptoms suggestive of hepatitis should have an unscheduled visit. Subjects with ALT $>3 \times$ ULN with or without symptoms should also have an unscheduled visit. A repeat assessment should be performed as soon as possible to confirm the finding. A clinical evaluation should be performed, including assessment of past medical history (including non-alcoholic fatty liver disease/steatohepatitis and alcohol use) and concomitant medications (including over the counter drugs and herbal supplements). Risk factors for hepatitis infection should be reviewed and hepatitis studies should be performed.

Study drug should be temporarily discontinued during this evaluation if the subject has signs or symptoms of hepatitis or an ALT $>5 \times$ ULN. The possible dosing re-initiation (re-challenge) or follow-up schedule for any events meeting these criteria will be determined by the Investigator in consultation with the Medical Monitor.

Recommended Hepatic Discontinuation Criteria

Study drug should be discontinued permanently if one of the following occurs (as confirmed by repeat assessment) and if the event is without an alternative explanation:

- ALT or aspartate aminotransferase (AST) $>8 \times$ ULN;
- ALT or AST $>5 \times$ ULN for more than 2 weeks;

- ALT or AST $>3 \times$ ULN and either total bilirubin $>2 \times$ ULN or international normalized ratio >1.5 ; and/or
- ALT or AST $>3 \times$ ULN with the appearance of fatigue, nausea, vomiting, right upper quadrant pain or tenderness, fever, rash, and/or eosinophilia ($>5\%$).

It is also recommended that statin regimen is discontinued. Abnormal values should be followed until they return within normal range or to a level deemed acceptable by the Investigator, or until the abnormality is explained by an appropriate diagnosis.

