4.3 Withdrawal Criteria

Participation of a subject in this clinical study may be discontinued for any of the following reasons:

- The subject withdraws consent or requests discontinuation from the study for any reason;
- Occurrence of any medical condition or circumstance that exposes the subject to substantial risk and/or does not allow the subject to adhere to the requirements of the protocol;
- Any SAE, clinically significant adverse event, severe laboratory abnormality, concomitant illness, or other medical condition which indicates to the Investigator that continued participation is not in the best interest of the subject;
- Pregnancy;
- Requirement of prohibited concomitant medication which is prohibited by the protocol;
- Subject failure to comply with protocol requirements or study-related procedures; or
- Termination of the study by the Sponsor or the regulatory authority.

If a subject withdraws prematurely from the study due to the above criteria or any other reason, study staff should make every effort to complete the full panel of assessments scheduled for the Early Termination (ET) Visit. The reason for subject withdrawal must be documented in the electronic Case Report Form (eCRF).

In the case of subjects lost to follow-up, attempts to contact the subject must be made and documented in the subject's medical records.

Withdrawn subjects will not be replaced. The sample size calculation accounts for a 10% dropout rate in the study.

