Any medical condition already present prior to the subject taking the first dose of study drug (Day 1) should be reported in the medical history. Any SAEs occurring prior to the first dose of study drug (Day 1) should be reported as an update to medical history as well as an adverse event. Any pre-existing medical condition or signs or symptoms that changes in severity, frequency, or seriousness after the subject takes the first dose of study drug (Day 1) and through the Follow-up Visit should be reported as an adverse event.

Clinically significant abnormal laboratory values or other examinations (e.g., ECG) that are detected at the time of the first dose of study drug (Day 1) and worsen during the study should be reported as adverse events. An abnormal laboratory result that is not verified by repeat testing does not necessitate reporting as an adverse event. The Investigator will exercise his or her medical, scientific, and clinical judgment in deciding whether an abnormal laboratory finding or other abnormal assessment is clinically significant. Clinically significant abnormal laboratory values occurring during the clinical study will be followed until repeat tests return to normal, stabilize, or are no longer clinically significant. Any abnormal test that is determined to be an error does not require reporting as an adverse event.

An overdose is a deliberate or inadvertent administration of a treatment at a dose higher than specified in the protocol and higher than known therapeutic doses. Overdoses with associated symptoms are always handled as AEs and reported as such. Overdoses without associated symptoms are not reported as AEs but are documented in EDC in order to collate information for the IB regarding the level of excess dosage taken or administered without adverse effects. An overdose will be reported irrespective of outcome even if toxic effects were not observed.

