8.1.4.3 Possible muscle and liver injury

For muscle injury, CK, hepatic, and renal function laboratory data will be integrated with myopathy signs and symptoms. For management of CK elevations $>3 \times$ ULN, refer to [Appendix E](#). For liver injury, laboratory data will be integrated with hepatic signs and symptoms. Alanine aminotransferase increases $>2 \times$ ULN with symptoms of hepatitis or $>3 \times$ ULN with or without symptoms of hepatitis will be evaluated and managed according to guidelines.

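### Appendix E holds study drug on ALT or symptoms only, although its permanent-stop list also uses AST, bilirubin and INR, so some asymptomatic stop-level first results carry no explicit hold

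*Protocol*

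**What the plan says.** Appendix E (Hepatic Monitoring) sets three steps.

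- **Work-up.** Subjects with signs or symptoms suggesting hepatitis get an unscheduled visit and chemistry panel. The enzyme triggers for a visit are ALT >2 × ULN with symptoms, or ALT >3 × ULN regardless of symptoms. Then: "A repeat assessment should be performed as soon as possible to confirm the finding". Section 8.1.4.3 repeats the ALT-only triggers; ALT above 3 × ULN "with or without symptoms of hepatitis will be evaluated and managed according to guidelines".
- **Temporary hold.** "Study drug should be temporarily discontinued during this evaluation if the subject has signs or symptoms of hepatitis or an ALT" is above 5 × ULN.
- **Permanent stop (Recommended Hepatic Discontinuation Criteria).** "Study drug should be discontinued permanently if one of the following occurs (as confirmed by repeat assessment"), provided nothing else explains the event. The criteria apply to ALT or AST: >8 × ULN; >5 × ULN for more than 2 weeks; >3 × "ULN and either total bilirubin" >2 × ULN or INR >1.5; or >3 × ULN with listed symptoms or eosinophilia above 5%.

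Three general provisions sit behind these steps. Appendix E leaves hepatic enzyme elevations to standard of care and the Investigator's discretion, and adds: "Abnormal values should be followed until they return within normal range or to a level deemed acceptable by the Investigator". Section 8.1 says clinically significant abnormal "laboratory values occurring during the clinical study will be followed until repeat tests return to normal, stabilize" or cease to be clinically significant. Section 4.3 allows withdrawal for "Any SAE, clinically significant adverse event, severe laboratory abnormality, concomitant illness" and similar, on the Investigator's judgement.

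**The concern.** A hold should catch at least every result that could become a permanent stop once confirmed. This one does not. AST, bilirubin and INR can each help end treatment for good, yet none of them prompts a pause while the confirming repeat is pending. AST alone can meet a stop criterion, but no AST value calls for the repeat by any stated time.

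Elsewhere the plan treats the two enzymes alike. Exclusion 1 (Section 4.2) and SAP Table 3 (Section 12.2) both use >2 × ULN for AST and for ALT. SAP Section 6.3 singles out hepatic toxicity, naming ALT/AST and bilirubin, for particular attention, and every subject also takes a statin.

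What is at stake is subject safety and consistent practice across about 20 sites. No efficacy estimate is affected.

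**Working it through.** The plan states no figure to reproduce here, so the check is one of rule logic for a single first result.

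**Inputs (Appendix E).** ALT and AST each in five bands (≤2, 2–3, 3–5, 5–8, >8 × ULN), bilirubin >2 × ULN yes/no, INR >1.5 yes/no, and symptoms yes/no. This gives 5 × 5 × 2 × 2 = 100 combinations without symptoms and 100 with. The criterion of >5 × ULN for more than 2 weeks is left out because one result cannot meet it. Eosinophilia is added at the end.

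**Rules as written**

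- Work-up (visit and prompt repeat) = symptoms, or ALT >3.
- Hold = symptoms, or ALT >5.
- Stop level = max(ALT, AST) >8; or max(ALT, AST) >3 with bilirubin >2, INR >1.5 or symptoms.

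**Examples, all asymptomatic** (bilirubin and INR below their cut-offs unless shown)

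| First result (× ULN; INR as value) | Stop level | Visit and prompt repeat | Hold |
|---|---|---|---|
| ALT 6, AST 1 | no | yes | yes |
| ALT 4, AST 2.5, bilirubin 2.5 | yes | yes | **no** |
| ALT 4, AST 1, INR 1.6 | yes | yes | **no** |
| ALT 4, AST 9 | yes | yes | **no** |
| ALT 2.5, AST 4, bilirubin 2.5 | yes | **no** | **no** |
| ALT 1, AST 9 | yes | **no** | **no** |

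**Stop-level combinations, asymptomatic**

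- Either enzyme >8: 25 − 16 = 9 ALT/AST pairs, × 4 bilirubin/INR states = 36.
- Higher enzyme between 3 and 8: 16 − 4 = 12 pairs, × 3 states with bilirubin or INR raised = 36.
- Total: 72.

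**Of these, without an explicit hold (ALT ≤5)**

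- ALT 3–5: AST >8 gives 4; the other four AST bands give 4 × 3 = 12. Total 16, all with a prompt repeat.
- ALT ≤3 (two bands): AST >8 gives 2 × 4 = 8; AST 3–5 or 5–8 gives 2 × 2 × 3 = 12. Total 20, none with an explicit visit or timed repeat.
- 16 + 20 = 36 of 72.

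**Restricted views**

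- AST ≤2 × ULN: 4 + 3 + 3 = 10 stop-level combinations; 3 lack a hold (ALT 3–5 with bilirubin or INR raised) and 0 lack a work-up.
- Symptomatic: 21 pairs × 4 = 84 stop-level combinations; 0 gaps, if the subject's symptoms are accepted as symptoms of hepatitis.
- Eosinophilia added (yes/no), asymptomatic: 156 stop-level combinations; 80 lack a hold, and 44 of those also lack a work-up.

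**Timing.** If no unscheduled repeat is done after Week 4 (Day 29), the next scheduled chemistry is Week 8 (Day 57): 57 − 29 = 28 days, or at most (57 + 3) − (29 − 3) = 34 days within the visit windows.

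**The case against.** The best counter-argument is that the subject is not abandoned.

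- **Backstops.** The stop list itself presupposes a repeat. Section 8.1 requires clinically significant values to be followed, and an AST above 8 × ULN is unlikely to be dismissed. The Appendix E paragraph opens with hepatic enzyme elevations in general, so its prompt repeat could be read to include AST. This stands in part: some repeat is implied. But the sentence follows ALT-specific triggers, so the AST reading is strained, and even that reading supplies no hold. None of the backstops sets a threshold, a time or a hold for these results.
- **The proportion.** Half of the combinations is not half of patients, and the ratio depends on the grid: 27 of the 36 gaps need AST in a higher band than ALT. With both enzymes in the same band, 10 combinations are at a stop level, 3 lack a hold and 0 lack a work-up. This stands. The counts show that the gap exists and where it lies; they say nothing about frequency.
- **Muscle-derived AST.** CK above 10 × ULN has its own visit and hold in Appendix E, which covers some AST-led cases. It does not cover those with lower CK, and it does not address the bilirubin and INR gap, which exists with normal AST.
- **Safety record.** Section 1.3 reports 837 multiple-dose subjects, no treatment-related SAE, and no hepatic event among the most common adverse events. The stop list is headed as a recommendation. That limits the urgency, but recommended steps should still agree with each other.
- **Undefined term.** Some sites may count raised bilirubin as a sign of hepatitis and hold drug. Because the term is undefined, others may not. The zero-gap result for symptomatic subjects rests on a generous reading of the same term.

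**Conclusion.** The concern holds. For asymptomatic subjects, Appendix E's hold does not cover its own permanent-stop criteria. ALT of 3–5 × ULN with bilirubin >2 × ULN or INR >1.5 gets a prompt repeat but no explicit hold. AST-led results at a stop level with ALT ≤3 × ULN get no explicit visit, timed repeat or hold. In the grid without eosinophilia these account for 36 of 72 stop-level combinations without a hold, 20 of them also without a work-up.

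The conclusion rests on reading the enzyme triggers as ALT-only, as they are written, and on not counting a laboratory bilirubin or INR value by itself as a sign of hepatitis. How often such results would occur cannot be judged from the documents. This is a safety wording gap that should be closed because it is cheap to close; it has no bearing on the efficacy analysis.

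**What to change.** Amend Appendix E and Section 8.1.4.3:

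1. Make the work-up triggers ALT **or AST**: >2 × ULN with symptoms, or >3 × ULN with or without symptoms.
2. Require a hold pending the repeat for signs or symptoms of hepatitis, for ALT **or AST** >5 × ULN, or for any first result that meets a permanent-stop criterion.

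Under these rules, stop-level combinations without a hold fall from 36 to 0, and those without a work-up from 20 to 0.

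**Cost.** No new assay is needed: AST, total bilirubin and INR are in the chemistry and coagulation panels drawn at every treatment visit (Section 8.6, Appendix B). Expect a few more unscheduled repeats and short holds, some of them for muscle-derived AST. In the asymptomatic grid without eosinophilia, 39 combinations become newly held: the 36 at a stop level and 3 that are not (AST 5–8 × ULN with ALT ≤5 × ULN and neither bilirubin nor INR raised).

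The hold would also act before alternative explanations are weighed. Subjects with Gilbert's syndrome may enter with raised bilirubin (exclusion 1), and anticoagulants are not named as excluded. Such subjects could therefore be held once ALT or AST passes 3 × ULN, if their standing bilirubin or INR already exceeds the cut-off. This is a small further cost and does not change the recommendation.
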